6.2 Common Items in Statistical Analysis

6.2.1 Patient Backgrounds

A list of patient backgrounds to be measured at enrollment is shown in Table 6-2. The details of categories when the background factors of continuous values among the background factors shown in Table 6-2 are divided by category are shown in Table 6-3.

Table 6-2 Background Factors

Item	Factor
Patient backgrounds	Sex, age, height, body weight, presence or absence of medical history, presence or absence of complications, race, ethnicity, and BMI
Disease characteristics	Timing of onset of lower urinary tract symptoms, presence or absence of pelvic visceral surgery, presence or absence of radiotherapy, presence or absence of drug therapy for the primary disease, bladder outlet obstruction index (males) ($P_{det}Q_{max} - 2Q_{max}$), prostate volume measurement (males), free Q_{max} , voiding time, voided volume (uroflowmetry), post void residual measured by ultrasonography, BVE (voided volume / [voided volume + post void residual] × 100), $P_{det}Q_{max}$, Q_{max} , BCI (males), PIP1 (females), IPSS total score, IPSS storage symptoms score, IPSS voiding symptoms score, IPSS (Q1, Q3, Q5, and Q6), presence or absence of CIC, presence or absence of bladder involuntary contraction, severity based on IPSS total score, severity based on IPSS QOLS score, and severity based on OABSS score

Table 6-3 Details of Categories

Category	Definition
Age category	< 60 years, ≥ 60 years < 65 years, ≥ 65 years < 70 years, ≥ 70 years < 75 years, ≥ 75 years
Race	Asian/Oriental, Other
Ethnicity	Japanese, .Other

6.2.2 Statistical Methods

6.2.2.1 Summary Statistics of Continuous Variables

Summary statistics of continuous variables will be presented together with the sample size, minimum, maximum, first quartile, median, third quartile, mean, and standard deviation.

6.2.2.2 Estimation Method

(1) Confidence interval of proportion

The confidence interval of proportion will be determined by an exact method based on F distribution.²⁾

The upper confidence limit P_U and the lower confidence limit P_L will be estimated using the following formula. P is the proportion, X is the number of patients with events, N is the number of patients in the analysis set, and α is the two-sided significance level.

$$P = X / N$$
$$P_U = \frac{\nu_1 F_{\nu_1, \nu_2}(\alpha/2)}{\nu_2 + \nu_1 F_{\nu_1, \nu_2}(\alpha/2)}, \quad \begin{aligned} \nu_1 &= 2(X + 1) \\ \nu_2 &= 2(N - X) \end{aligned}$$

$$P_L = \frac{\nu_2}{\nu_2 + \nu_1 F_{\nu_1, \nu_2}(\alpha/2)}, \quad \begin{aligned} \nu_1 &= 2(N - X + 1) \\ \nu_2 &= 2X \end{aligned}$$

6.2.3 Allocation Adjustment Factors to Be Used for Analysis

In the analysis using allocation adjustment factors, the data of allocation adjustment factors at the time of enrollment will be used.

Allocation adjustment factors are shown below.

- Sex (male or female)
- Age at informed consent (< 65 years or \geq 65 years)

6.2.4 Statistical Analysis Software

In this study, all statistical processing will be performed using SAS Version 9.4 (SAS/STAT 14.2).

7. Primary Endpoint Analyses

The items to be analyzed for the primary endpoint are summarized below.

7.1 Primary Analysis Corresponding to the Primary Objective

For BCI (males) and PIP1 (females), summary statistics and 95% confidence intervals for each evaluation time point (Weeks 0 and 12) were calculated by group in the PPS.

7.2 Sensitivity Analysis of Primary Analysis

The primary analysis will be performed in the FAS.

7.3 Secondary Analyses of the Primary Endpoint

For BCI (males) and PIP1 (females), the following analyses will be performed in the FAS and PPS.

- Time course plots at each evaluation time point (Weeks 0 and 12) will be prepared by group.
- Paired t-tests for the measured values at baseline (Week 0) and Week 12 of the treatment period will be performed by group.
- Summary statistics and 95% confidence intervals for the change and percentage change at Week 12 of the treatment period relative to baseline (Week 0) will be calculated by group.

- For the measured values at each evaluation time point (Weeks 0 and 12) and the change and percentage change from baseline (Week 0) to Week 12 of the treatment period, the 95% confidence interval for the difference between the placebo group and the TAC-302 group will be calculated.
- For the change and percentage change from baseline (Week 0) to Week 12 of the treatment period, student's t test will be performed using the placebo group as the control.
- Analysis of covariance of the change and percentage change from baseline (Week 0) to Week 12 of the treatment period will be performed using treatment group, baseline value, and age (< 60 years or \geq 60 years in males, < 70 years or \geq 70 years in females) as covariates, and the least squares means in each treatment group, and the difference in least squares mean between the placebo group and the TAC-302 group and its two-sided 95% confidence interval will be estimated.
- By age (< 60 years and \geq 60 years in males and < 70 years and \geq 70 years in females), the above analysis excluding time course plots and analysis of covariance will be performed.

8. Secondary Endpoint Analyses

The analyses of the secondary endpoints are outlined below.

8.1 Analysis of Efficacy

In principle, the following analyses will be performed by treatment group in the FAS and PPS.

8.1.1 Pressure Flow Study (PFS) Parameters (Filling Phase)

For the volume at first desire to void, maximum bladder volume, bladder compliance, and bladder volume up to appearance of bladder involuntary contraction, the following analyses 1) to 5) will be performed. In addition, the analysis in 6) will be performed.

- 1) Summary statistics and 95% confidence intervals for the measured values at each evaluation time point (Weeks 0 and 12), and for the change and percentage change at Week 12 of the treatment period relative to baseline (Week 0), will be calculated.
- 2) Paired t-test for the measured values at baseline (Week 0) and Week 12 of the treatment period will be performed.
- 3) For the measured values at each evaluation time point (Weeks 0 and 12) and the change and percentage change from baseline (Week 0) to Week 12 of the treatment period, the 95% confidence interval for the difference between the placebo group and the TAC-302 group will be calculated.
- 4) For the change and percentage change from baseline (Week 0) to Week 12 of the treatment period, student's t test will be performed using the placebo group as the control.
- 5) Analysis of covariance of the change and percentage change from baseline (Week 0) to Week 12 of the treatment period will be performed using treatment group, baseline value, and age (< 65 years or \geq 65 years) as covariates, and the least squares means in each treatment group, and the difference in least squares mean between the placebo group and the TAC-302 group and its two-sided 95% confidence interval will be estimated.
- 6) The frequency of involuntary bladder contractions at each evaluation time point (Weeks 0 and 12) will be tabulated.

8.1.2 Pressure Flow Study (PFS) Parameters (Voiding Phase)

The following analyses will be performed for the detrusor pressure at start of voiding ($P_{det\ open}$), maximum detrusor pressure ($P_{det\ max}$), maximum flow rate (Q_{max}), average flow rate (Q_{ave}), detrusor pressure at maximum flow rate ($P_{detQ_{max}}$), duration of bladder contraction, voided volume, and post void residual.

- 1) Summary statistics and 95% confidence intervals for the measured values at each evaluation time point (Weeks 0 and 12), and for the change and percentage change at Week 12 of the treatment period relative to baseline (Week 0), will be calculated.
- 2) Paired t-test for the measured values at baseline (Week 0) and Week 12 of the treatment period will be performed.
- 3) For the measured values at each evaluation time point (Weeks 0 and 12) and the change and percentage change from baseline (Week 0) to Week 12 of the treatment period, the 95% confidence interval for the difference between the placebo group and the TAC-302 group will be calculated.
- 4) For the change and percentage change from baseline (Week 0) to Week 12 of the treatment period, student's t test will be performed using the placebo group as the control.
- 5) Analysis of covariance of the change and percentage change from baseline (Week 0) to Week 12 of the treatment period will be performed using treatment group, baseline value, and age (< 65 years or \geq 65 years) as covariates, and the least squares means in each treatment group, and the difference in least

squares mean between the placebo group and the TAC-302 group and its two-sided 95% confidence interval will be estimated.

6) A scatter plot with Q_{\max} on the vertical axis and $P_{\text{det}}Q_{\max}$ on the horizontal axis will be prepared for each sex.

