3. STUDY DESIGN

This study is a central-registration, multi-center, double-blind, placebo-controlled, randomized parallel-group comparative study to investigate the efficacy and safety of TAC-302 in DU patients with OAB. The design of this study is shown in [Figure 3-1](#). This study is composed of a single-blind observation period, a double-blind treatment period, and a follow-up period.

Patients considered eligible for the enrollment in the observation period after providing written informed consent will proceed to the observation period. The investigational drug for the observation period will be administered under single-blind conditions. In the observation period, the investigational drug (placebo) will be administered orally twice daily after breakfast and dinner for 2 to 4 weeks. Patients considered eligible for the enrollment in the treatment period after the end of the observation period will proceed to the treatment period. The investigational drug for the treatment period will be administered under double-blind conditions. The investigational drug in the treatment period will be randomly assigned, with patients allocated to the TAC-302 and placebo group in a 2:1 ratio. To maintain a balance between groups, dynamic assignment using assignment factors [sex (male and female), age at informed consent (< 65 years and \geq 65 years)] will be performed. In the treatment period, the investigational drug (TAC-302 200 mg or placebo) will be administered orally twice daily after breakfast and dinner for 12 weeks. After the start of the treatment period (registration in the treatment period), patients will make visits in weeks 2, 4, 8, and 12, and the designated observations and tests will be performed. A follow-up examination will be performed 1 week after the end of week 12 of the treatment period. If any adverse event is considered to be an adverse reaction after the follow-up examination, the follow-up investigation should be performed until it is confirmed that the symptom (including abnormal laboratory values) has recovered to the state of before the onset as much as possible or is resolving.

[figure not shown]

Figure 3-1 Study Design

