8.1.3 Uroflowmetry Parameters

The following analyses will be performed for the maximum flow rate (free Q_{\max}), average flow rate (free Q_{ave}), voided volume, and voiding time.

- 1) Summary statistics and 95% confidence intervals for the measured values at each evaluation time point (Weeks 0, 4, 8, and 12), and for the changes and percentage changes at Weeks 0, 4, 8, and 12 of the treatment period relative to baseline (Week 0), will be calculated.
- 2) Paired t-test for the measured values at baseline (Week 0) and Week 12 of the treatment period will be performed.
- 3) For the measured values at each evaluation time point (Weeks 0, 4, 8, and 12) and the changes and percentage changes from baseline (Week 0) to Weeks 4, 8, and 12 of the treatment period, the 95% confidence interval for the difference between the placebo group and the TAC-302 group will be calculated.
- 4) For the changes and percentage changes from baseline (Week 0) to each evaluation time point (Weeks 4, 8, and 12), student's t test will be performed using the placebo group as the control.
- 5) The same analyses as 1) to 4) will be performed for the case where missing data at Week 12 of the treatment period are imputed with the last observation carried forward (LOCF).

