8.1.4 Post Void Residual Measured by Ultrasonography

The following analyses will be performed for post void residual measured by ultrasonography.

- 1) Summary statistics and 95% confidence intervals for the measured values at each evaluation time point (Weeks 0, 4, 8, and 12), and for the changes and percentage changes at Weeks 0, 4, 8, and 12 of the treatment period relative to baseline (Week 0), will be calculated.
- 2) Paired t-tests for the measured values at baseline (Week 0) and Weeks 4, 8, and 12 of the treatment period will be performed.
- 3) For the measured values at each evaluation time point (Weeks 0, 4, 8, and 12) and the changes and percentage changes from baseline (Week 0) to Weeks 4, 8, and 12 of the treatment period, the 95% confidence interval for the difference between the placebo group and the TAC-302 group will be calculated.
- 4) For the changes and percentage changes from baseline (Week 0) to each evaluation time point (Weeks 4, 8, and 12), student's t test will be performed using the placebo group as the control.
- 5) The same analyses as 1) to 4) will be performed for the case where missing data at Week 12 of the treatment period are imputed with LOCF.
- 6) The change and percentage change from baseline (Week 0) will be analyzed by MMRM using treatment group, evaluation time point (Weeks 4, 8, and 12 of the treatment period), and interaction between treatment group and evaluation time point as fixed effects and baseline value, sex, and age (< 65 years or \geq 65 years) as covariates. The least squares means in each treatment group, and the difference in the least squares mean between the placebo group and the TAC-302 group and its two-sided 95% confidence interval at each evaluation time point will be estimated. Unstructured covariance structure will be assumed, and toeplitz type will be used if convergence is not achieved. If convergence is still not achieved, the first-order autoregressive, compound symmetry, and variance component will be used in this order. The Kenward-Roger method (2009)⁴⁾ will be used to calculate degrees of freedom.

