8.1.5 BVE [Voided Volume / (Voided Volume + Post Void Residual)]

The following analyses will be performed for BVE calculated from the voided volume measured by uroflowmetry and the post void residual measured by ultrasonography.

- 1) Summary statistics and 95% confidence intervals for the measured values at each evaluation time point (Weeks 0, 4, 8, and 12), and for the changes and percentage changes at Weeks 0, 4, 8, and 12 of the treatment period relative to baseline (Week 0), will be calculated.
- 2) Paired t-tests for the measured values at baseline (Week 0) and Weeks 4, 8, and 12 of the treatment period will be performed.
- 3) For the measured values at each evaluation time point (Weeks 0, 4, 8, and 12) and the changes and percentage changes from baseline (Week 0) to Weeks 4, 8, and 12 of the treatment period, the 95% confidence interval for the difference between the placebo group and the TAC-302 group will be calculated.
- 4) For the changes and percentage changes from baseline (Week 0) to each evaluation time point (Weeks 4, 8, and 12), student's t test will be performed using the placebo group as the control.
- 5) The same analyses as 1) to 4) will be performed for the case where missing data at Week 12 of the treatment period are imputed with LOCF.
- 6) The change and percentage change from baseline (Week 0) will be analyzed by MMRM using treatment group, evaluation time point (Weeks 4, 8, and 12 of the treatment period), and interaction between treatment group and evaluation time point as fixed effects and baseline value, sex, and age (< 65 years or ≥ 65 years) as covariates. The least squares means in each treatment group, and the difference in the least squares mean between the placebo group and the TAC-302 group and its two-sided 95% confidence interval at each evaluation time point will be estimated. Unstructured covariance structure will be assumed, and toeplitz type will be used if convergence is not achieved. If convergence is still not achieved, the first-order autoregressive, compound symmetry, and variance component will be used in this order. The Kenward-Roger method (2009) will be used to calculate degrees of freedom.

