8.1.9 Bladder Diary Records

The following analyses will be performed for the average number of micturitions per 24 hours, average number of urgency urinary incontinence episodes per 24 hours, average number of urinary urgency episodes per 24 hours, average voided volume per urination, average number of daytime urinations, and average number of nocturnal urinations.

- 1) Summary statistics will be calculated for the measured values at each evaluation time point (Weeks 0, 4, 8, and 12) and the changes and percentage changes from baseline (Week 0) to Week 4, 8, and 12 of the treatment period. The same analysis will be performed by presence or absence of CIC.
- 2) Paired t-tests for the measured values at baseline (Week 0) and Weeks 4, 8, and 12 of the treatment period will be performed.
- 3) For the measured values at each evaluation time point (Weeks 0, 4, 8, and 12) and the changes and percentage changes from baseline (Week 0) to Weeks 4, 8, and 12 of the treatment period, the 95% confidence interval for the difference between the placebo group and the TAC-302 group will be calculated. The same analysis will be performed by presence or absence of CIC.
- 4) For the changes and percentage changes from baseline (Week 0) to each evaluation time point (Weeks 4, 8, and 12), student's t test, Wilcoxon rank sum test, and van Elteren test using the allocation adjustment factors as strata⁵⁾ will be performed using the placebo group as the control.
- 5) The proportion of patients with a $\leq -50\%$ change in the average number of urgency urinary incontinence episodes per 24 hours will be calculated, and Fisher's exact test will be performed to compare the between-group difference.
- 6) The same analyses as 1) to 4) will be performed for the case where missing data at Week 12 of the treatment period are imputed with LOCF.

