8.1.10 Relationship Between Efficacy Endpoints

For the relationship of the change and percentage change from baseline (Week 0) to Week 12 of the treatment period between the efficacy endpoints, Pearson and Spearman correlation coefficients will be calculated, and scatter plots will be prepared. The combinations of endpoints to be evaluated are those for which a combination of diseases considered to be related (DU or DU-OAB) is specified in Figure 8-1.

Figure 8-1 Combinations of Efficacy Endpoints for Which the Relationship of Change and Percentage Change from Baseline (Week 0) to Week 12 of the Treatment Period Will Be Evaluated

		Pressure Flow Study						Uroflowmetry			
		BCI (males)	PIP1 (females)	Q _{max} (analyzed separately for males and females)	P _{det} Q _{max} (analyzed separately for males and females)	Duration of bladder contraction -1 (analyzed overall and separately for males and females)	Duration of bladder contraction -2 (analyzed overall and separately for males and females)	free Q _{max} (analyzed separately for males and females)	free Q _{ave} (analyzed separately for males and females)	Voided volume (analyzed overall and separately for males and females)	Voiding time (analyzed overall and separately for males and females)
Pressure Flow Study	BCI										
	PIP1										
	Q _{max}										
	P _{det} Q _{max}										
	Duration of bladder contraction-1	DU	DU								
	Duration of bladder contraction-2	DU	DU								
Uroflow- metry (uroflow metry)	free Q _{max}	DU	DU	DU	DU						
	free Q _{ave}	DU	DU								
	Voided volume	DU	DU	DU	DU	DU	DU				
	Voiding time	DU	DU	DU	DU	DU	DU				
Other Endpoints	Post void residual measured by ultrasonography	DU	DU	DU	DU	DU	DU	DU	DU	DU	DU
	BVE	DU	DU	DU	DU	DU	DU	DU	DU		DU
	IPSS total score	DU	DU	DU	DU	DU	DU	DU	DU		DU
	IPSS voiding symptoms score	DU	DU	DU	DU	DU	DU	DU	DU		DU
	IPSS (Question 1)	DU	DU	DU	DU	DU	DU	DU	DU		DU
	IPSS (Question 3)	DU	DU	DU	DU	DU	DU	DU	DU		DU
	IPSS (Question 5)	DU	DU	DU	DU	DU	DU	DU	DU		DU
	IPSS (Question 6)	DU	DU	DU	DU	DU	DU	DU	DU		DU
	IPSS storage symptoms score	DU-OAB	DU-OAB					DU-OAB			
Bladder Diary records	OABSS	DU-OAB	DU-OAB					DU-OAB			
	Average number of micturitions per 24 hours	DU-OAB	DU-OAB					DU-OAB			DU-OAB
	Average number of urinary urgency episodes per 24 hours	DU-OAB	DU-OAB					DU-OAB			
Average voided volume per urination		DU-OAB	DU-OAB					DU-OAB			DU-OAB

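### The both-sex ANCOVAs for pressure flow parameters (SAP 8.1.1 and 8.1.2) omit sex, a minimisation factor that all five both-sex MMRMs include, and no reason is given

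*SAP*

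**What the plan says.** Protocol section 3 describes "dynamic assignment using assignment factors [sex (male and female), age at informed consent" (under 65, or 65 and over)], and Protocol 3.2.1 specifies 2:1 minimisation with a random element. SAP 6.2.3 names the same two factors and says: "In the analysis using allocation adjustment factors, the data of allocation adjustment factors at the time of enrollment will be used".

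SAP 8.1 runs its analyses by treatment group in the FAS and PPS; by-sex repeats come separately in 8.1.11. For the filling-phase and voiding-phase pressure flow parameters, the ANCOVA of change and percentage change "will be performed using treatment group, baseline value, and age (< 65 years" or 65 and over) as covariates. The MMRM in 8.1.4 instead takes treatment, visit and their interaction "as fixed effects and baseline value, sex, and age (< 65 years" or 65 and over) as covariates, and 8.1.5, 8.1.6, 8.1.7 and 8.1.9 repeat that list. Section 8.1.9 also has a "van Elteren test using the allocation adjustment factors as strata".

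For uroflowmetry (8.1.3), the between-arm analyses are an unadjusted interval and a test on change: "student's t test will be performed using the placebo group as the control". Both are repeated with LOCF. KHQ (8.1.8) has the same interval and test without LOCF. Neither section lists a model with a baseline covariate.

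**The concern.** A factor used to balance the arms would normally be in the model that compares them. Here the pressure flow ANCOVAs keep one minimisation factor (age) and drop the other (sex), while every both-sex MMRM keeps both. When allocation has balanced sex and the model ignores it, any variation in outcome due to sex is counted as noise. The reported standard error then exceeds the true one, and intervals and tests become conservative.

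Comparison with placebo is a stated secondary objective (Protocol 2.2, SAP 1.2), so these estimates will be read. The stake is modest: some precision, and consistency across secondary endpoints of a phase 2a trial.

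**Working it through.** **1. Covariates side by side (models fitted to both sexes).**

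| SAP section | Endpoint | Between-arm model | Baseline | Age 65 | Sex |
|---|---|---|---|---|---|
| 8.1.1 item 5 | PFS, filling | ANCOVA | yes | yes | **no** |
| 8.1.2 item 5 | PFS, voiding | ANCOVA | yes | yes | **no** |
| 8.1.3 | Uroflowmetry | none listed | – | – | – |
| 8.1.4 item 6 | Post void residual | MMRM | yes | yes | yes |
| 8.1.5 item 6 | BVE | MMRM | yes | yes | yes |
| 8.1.6 item 6 | IPSS | MMRM | yes | yes | yes |
| 8.1.7 item 6 | OABSS | MMRM | yes | yes | yes |
| 8.1.8 | KHQ | none listed | – | – | – |
| 8.1.9 item 7 | Bladder diary | MMRM | yes | yes | yes |

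The ANCOVAs in 7.3 (BCI in males, PIP1 in females) are single-sex and outside the point. The plan states no figure to reproduce, and its sample-size rationale is redacted.

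**2. Size of the omission.** From SAP 2.2.1 there are 48 males and 27 females, so p = 48/75 = 0.64 and pq = 0.64 × 0.36 = 0.2304. Let g be the sex effect on change at a given baseline, in residual SDs, and d the sex difference at baseline, in SDs. Both are assumptions. Without sex in the model, the interval is wider by about

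√(1 + g²·pq/(1 + pq·d²)), less the cost of estimating one more coefficient.

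- g = 0.5, d = 0: √(1 + 0.25 × 0.2304) = 1.028
- g = 1.0, d = 0: √1.2304 = 1.109
- g = 1.0, d = 3: 0.2304/3.0736 = 0.0750; √1.0750 = 1.037

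A simulation of 6,000 trials over 3,000 minimised 2:1 allocations checks this. It assumes 65% aged 65 or over, baseline slope −0.4, residual SD 1 and no treatment effect. Results without sex relative to with sex:

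| | d = 0 | d = 1 | d = 2 | d = 3 |
|---|---|---|---|---|
| CI wider, g = 0.5 | 2.9% | 2.2% | 1.1% | 0.5% |
| CI wider, g = 1.0 | 11.1% | 8.9% | 5.5% | 3.2% |
| True SD larger, g = 0.5 | 0.2% | 0.5% | 0.5% | 0.5% |
| True SD larger, g = 1.0 | 1.0% | 2.2% | 2.9% | 2.4% |

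Another run gave 0.3% at g = 0.5, d = 3, hence the range 0.3 to 2.9%. Coverage was 94.8 to 97.0% without sex and 94.7 to 95.3% with it; mean bias was at most 0.004 SD. With no sex effect, leaving sex out narrows the interval by 0.1 to 0.5%, which is the whole cost of adding it.

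A separately built simulation (4,000 runs per setting) was indexed by the share of residual variance due to sex. At 5% and 20% the interval was 2.6% and 12.1% wider, with type I error 0.043 and 0.024 against a nominal 0.05. With sex included, type I error was 0.046 to 0.050.

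**3. What the by-sex ANCOVAs already hold.** At 2:1 the target cells are 32/16 males and 18/9 females. Information on the treatment difference adds up exactly: 1/(1/32 + 1/16) + 1/(1/18 + 1/9) = 10.67 + 6.00 = 16.67 = 1/(1/50 + 1/25). In simulation, a precision-weighted combination of the two by-sex ANCOVAs has an SD 3.0 to 3.8% larger than the pooled ANCOVA with sex when residual SDs are equal. It is 5 to 18% smaller when the female residual SD is 1.5 or 0.5 times the male. The SAP specifies no such combination.

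**4. Uroflowmetry and KHQ.** With ρ the baseline to follow-up correlation and k the ratio of follow-up to baseline SD, the width of the change-score interval relative to baseline ANCOVA is √[(1 + k² − 2ρk)/(k²(1 − ρ²))]. For example, at k = 1, ρ = 0.3: √(1.4/0.91) = 1.240.

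| | ρ = 0.3 | 0.5 | 0.7 | 0.9 |
|---|---|---|---|---|
| k = 1 | 1.240 | 1.155 | 1.085 | 1.026 |
| k = 1.25 | 1.129 | 1.058 | 1.010 | 1.026 |
| k = 0.8 | 1.411 | 1.323 | 1.262 | 1.282 |

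Against a simulated Week 12 MMRM with baseline, sex and age (complete data, equal correlation between visits), the change-score interval is 1 to 22%, −1 to 11% and 24 to 39% wider respectively. The documents give neither ρ nor k. All figures in steps 2 to 4 are for change, not percentage change, and for continuous outcomes.

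**The case against.** The best defence is that the trial reads pressure flow results by sex. It has different primary endpoints and urodynamic entry limits for men and women, 8.1.2 item 6 plots by sex, and 8.1.10 analyses Qmax and PdetQmax by sex only. Section 8.1.11 repeats the ANCOVAs within each sex, and step 3 shows that little information is lost. This stands, and it is the main reason the point is small. It does not explain why a both-sex ANCOVA is specified at all and then leaves sex out. Section 8.1.10 also lists "Duration of bladder contraction -1 (analyzed overall and separately for males and females"), and contraction duration is an 8.1.2 parameter. That figure concerns correlations rather than treatment effects, so it is limited support.

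It is also fair that no stated rule is broken. SAP 6.2.3 says which data to use when allocation factors are used; a reader might infer that every model must contain both, but it does not say so. Protocol 13.1.3.3 promises only by-group summaries for these endpoints (with intervals for most), and the SAP goes beyond that. SAP 11.1 leaves covariate details to be given separately, and section 12 leaves the full list of analyses to a report analysis plan that is not among these documents. So one can say only that the SAP lists no such model, not that none exists.

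For uroflowmetry and KHQ, the case for a model is one of consistency. "The following analyses will be performed for BVE calculated from the voided volume measured by uroflowmetry" and it has an MMRM, whereas the voided volume itself has none. Against that, the change-score t-test is valid, the larger gains need a follow-up SD below the baseline SD, and several KHQ domains are coarse: two rest on a single item and one can be not applicable. That part is therefore optional.

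**Conclusion.** The omission of sex from the two both-sex ANCOVAs is real and unexplained, and its consequence is minor. Under assumed sex effects of 0.5 to 1.0 residual SD, intervals are 0.3 to 11% wider. Most of that is over-coverage, since the true SD rises only 0.2 to 2.9%. If sex does not predict change, nothing is lost.

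Several stronger readings are not supported:
- That the pressure flow estimates are biased: minimisation balances sex, and the simulated bias is negligible.
- That every MMRM in the SAP contains sex: this is true of the five fitted to both sexes. The by-sex repeats in 8.1.11 use baseline and age only, as they must.
- That the primary result is affected: the analysis in 7.1 is descriptive, and the ANCOVAs in 7.3 are single-sex.
- That the omission is proven to be a slip: the SAP's change table shows superseded 8.1.11 wording that removed sex from by-sex ANCOVAs, but superseded text does not establish intent.
- That the uroflowmetry and KHQ t-tests are wrong: they are valid, and the gain from a model can be nil.

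**What to change.** Main change: in 8.1.1 and 8.1.2, item 5, add sex to the covariates whenever both sexes are in the model. State that sex is dropped from every by-sex repeat (8.1.11, 8.1.14, 8.1.15). The second sentence is needed because 8.1.14 and 8.1.15 switch off models only in 8.1.1, 8.1.4 and 8.1.5. Read literally, the 8.1.2 ANCOVA still runs there by sex, where sex would be a constant. The cost is wording and one degree of freedom, at most about 0.5% of interval width.

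Optional change: for 8.1.3 add the MMRM of 8.1.4 item 6; for 8.1.8 add an ANCOVA with treatment, baseline, sex and age. Keep the t-tests as supportive. Run the new models in the FAS and PPS overall, and by sex under the 8.1.11 covariates. Add 8.1.3 to the sections for which 8.1.14 and 8.1.15 perform no MMRM. The downside is more output: (4 uroflowmetry parameters + 9 KHQ domains) × 2 (change, percentage change) × 2 (FAS, PPS) = 52 fits, plus 52 × 2 = 104 by sex. No new data are needed.

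If these models are already in the report analysis plan, cite them in the SAP. If they are added after unblinding, label them as newly planned, as SAP section 10 requires.
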